### 3.4 Withdrawal and discontinuation

Participants are free to withdraw their consent at any time without giving any reason. In case of withdrawal of consent, their sample will be destroyed and their data will be deleted from the database.

## 4 STATISTICS AND METHODOLOGY

### 4.1. Statistical analysis plan

#### 4.1.1 Randomization

To ensure allocation concealment, randomization will be performed with a block of 170 in a 1:1 allocation ratio by a web-based independent randomization software (Random Allocation version 1.0). Patients will be randomly assigned to either OP+N GSS or to OP+N USS. Instruction on the assigned procedure will be kept in sealed opaque envelopes labeled with sequential study numbers and opened right before swab-testing.

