### 2.3.2. Randomized telemedical and HCP sampling

After giving informed consent by signing the consent form, patients will be randomized to either OP+N GSS - or to OP+N USS.

After performing either procedure, they will continue to be sampled by HCP OP+N and HCP NP.

[figure not shown]
We will start the assessment with the self-sampling methods in order to reduce bias that could occur if they experience the HCP's sampling.

Written instructions on how to perform a self-test will be provided, representing the instructions that come along with a commercially available rapid test set. An instructional online video tutorial or similar would also account as the latest state of the art. However, this has not yet been implemented comprehensively with all available test sets that are currently being distributed across Switzerland.

Furthermore, to avoid bias in the sampling procedure, exclusively one HCP at the testing station will be designated as the study's sampling expert. The HCP will perform the NP and OP+N sampling sequentially in a previously randomized order.

The telemedical guidance will be exclusively done by the same HCP in order to minimize interoperability differences. The standardized telemedical sampling will be conducted at the same test station, in a separate empty room in which a computer will be placed with instructions on how to connect for the telemedical consultation.

Figure 1: Study chart

During each sampling procedure, the patients will either undergo OP+N GSS or OP+N USS for PCR analysis, as well as for antigenic testing. This means each participant will be sampled a total of six times within 15 minutes from different locations in the upper respiratory tract. Concordance of results between sampling by GSS vs. USS vs. HCPs will be assessed.

As the difference in time between the samplings can influence the Ct value, the sampling process will only be started when the HCP and the telemedical supervisor are ready. The three different samples will be stored in the test station refrigerator between 2°C-8°C before transport.

A grouping of samples will ensure that temperature changes are consistent between samples from the same participant.

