#### 3.2 Recruitment, screening and informed consent procedure

The participating test station in Olten receives approximately 100 patients per day for PCR and/or antigen testing. The population is mixed as both asymptomatic people, as well as symptomatic people, frequent the facility for SARS-CoV-2 testing. The recruitment will happen by the local investigator in daily clinical practice. All costs for tests performed within the framework of the study will be financed by the study. A payable travel certificate will be issued for unchanged costs. Participation in the study and spending time on it is voluntary, free of charge and at no cost to the study participants. However, each study participant will receive a voucher for free PCR testing at a later date.

Patients who wish to have a COVID test can register online at least one day in advance for predefined time slots for appointments (via the Onedoc-Software, Geneva, Switzerland).

Immediately after registration, the potential test participants will be informed about the study either by telephone or by e-mail based on their contact details, with delivery of the written study material if they are interested, giving them more than 24 hours to contemplate whether they want to participate.

At the consultation, a personal oral and written briefing about the study goals and study design, as well as the informed consent form will be given to the participants. They are invited to date and sign if they are willing to participate and have no further questions, and express to have understood the content and do agree with it. A copy of the signed document will be given to the study participant. The consent form will be stored as part of the study records.

Participants will not receive financial compensation for the participation in this study. However, each study participant will receive a voucher for free PCR testing at a later date.

We shall end recruiting either when reaching the necessary sample size or no later than October 30th, 2022.

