#### 4.1.2 Sample size

The SD of the mean of Ct values for RT-PCR analysis of multiple samples is not clearly defined in the literature and varies between studies.

If there is truly no difference between the standard and experimental treatment, then 85 patients per group are required to be 90% sure that the lower limit of a one-sided 97.5% confidence interval (or equivalently a 95% two-sided confidence interval) will be above the non-inferiority limit of -3.

We, therefore, estimated a standard error of six that accounts for this variance. In addition, the limit of non-inferiority was set at three according to clinical significance.

Results will be stratified by symptom status, age, and sex.

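### One unstratified block of 170 leaves balance between guided and unsupervised self-sampling unenforced at an early stop, over time and by symptom status: a minor precision issue for that comparison only

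*Combined protocol and SAP*

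**What the plan says.** Section 4.1.1 (Randomization) states that "randomization will be performed with a block of 170 in a 1:1 allocation ratio". It describes one assignment: "Patients will be randomly assigned to either OP+N GSS or to OP+N USS". No stratification factor is named. Assignments are kept in sealed, opaque, sequentially numbered envelopes.

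Section 4.1.2 (Sample size) gives the total: "85 patients per group are required to be 90% sure that the lower limit of a one-sided 97.5% confidence interval" "will be above the non-inferiority limit of -3". Twice 85 is 170, so the block and the planned sample are the same.

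Section 3.2 sets two ways to stop: "We shall end recruiting either when reaching the necessary sample size or no later than October 30th, 2022". It also says that both symptomatic and asymptomatic people attend the test station, without giving the proportions.

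On symptoms, section 4.1.2 says "Results will be stratified by symptom status, age, and sex". Section 4.1.4 assigns the handling of confounders to logistic regression. Shell Table 1 in the Appendix, which lists potential confounders, contains neither symptom status nor calendar time.

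Section 2.1 lists superiority of GSS over USS as one of three hypotheses. Section 4.1.3 contains no GSS versus USS test; its three comparisons are all between samples from the same participant.

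**The concern.** A permuted block forces equal arms only when it is complete. With one block for the whole trial that happens once, at participant 170. If recruitment ends by date, the arms may differ in size. Even with all 170 randomised, nothing makes the arms similar in symptom mix or spreads each arm evenly over the recruitment period.

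This bears on GSS versus USS, where different people are compared. Symptom status may be related to viral load and so to Ct. Section 1 describes the emergence of a variant with increased viral load, so calendar time may be related to Ct as well. A chance difference in either would enter the GSS versus USS estimate, and the plan prespecifies no adjusted analysis of it. Logistic regression, the method named in section 4.1.4, does not directly adjust a difference in a continuous Ct value.

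**Working it through.** **1. The plan's own figure.** Inputs from section 4.1.2: margin 3, true difference 0 ("If there is truly no difference between the standard and experimental treatment"), one-sided 0.025, power 90%, and a spread of 6. The text calls the 6 a standard error, but it reproduces the sample size only if read as an SD.

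n per group = 2 × 6² × (1.960 + 1.282)² / 3² = 84.06, rounded up to 85. Total 170, equal to the block. Power at 85 per group is 90.3%.

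**2. Arm sizes if recruitment stops after m participants.** Under one block of 85 + 85, the number in one arm is hypergeometric(170, 85, m). The SD of the difference in arm sizes is 2 × √[m × ¼ × (170 − m)/169].

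| m | SD of difference | Central 95% split | Chance of a difference of 10 or more |
|---|---|---|---|
| 85 | 6.5 | 36:49 | 12.5% |
| 100 | 6.4 | 44:56 | 16% |
| 120 | 6.0 | 54:66 | 13% |
| 136 | 5.2 | 63:73 | 8% |
| 150 | 4.2 | 71:79 | 3% |
| 170 | 0 | 85:85 | 0 |

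The stopping points are scenarios; the documents give neither start date nor uptake.

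**3. What unequal arms cost.** With SD 6 and a distance of 3 Ct, power is Φ(3/SE − 1.96), where SE = 6 × √(1/a + 1/b). At m = 100 it is 70.5% for 50:50 and 69.9% for 44:56. At m = 85 it is 63.5% if balanced and 62.5% for 36:49. Nearly all the loss from 90.3% comes from the smaller total.

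**4. Symptom mix with all 170 randomised.** If S of 170 are symptomatic, the number in one arm is hypergeometric(170, 85, S). The share is not in the documents, so a range is assumed.

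| Symptomatic share (assumed) | S | SD of difference | Chance of a difference of 10 or more people |
|---|---|---|---|
| 10% | 17 | 3.9 | 0.9% |
| 20% | 34 | 5.2 | 8% |
| 30% | 51 | 6.0 | 9% |
| 40% | 68 | 6.4 | 16% |

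The step from 20% to 30% is small because an odd S allows only odd differences, so the threshold there is in effect 11.

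**5. Size in Ct.** A difference of 10 symptomatic people is 10/85 = 11.8 percentage points. If symptoms shift Ct by 2 to 5 cycles (assumed), the GSS-USS mean moves by 0.118 × 2 = 0.24 to 0.118 × 5 = 0.59 Ct. The standard error at 85 per arm is 6 × √(2/85) = 0.92. The shift is therefore 0.26 to 0.64 standard errors.

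**6. What adjustment gains.** The share of raw-Ct variance explained by symptom status is p(1 − p)δ²/36. For p = 0.4 and δ = 2 to 5 (both assumed) it is 0.24 × 4/36 = 2.7% to 0.24 × 25/36 = 16.7%. This gain comes from the covariate in the analysis and not from the blocking.

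**7. What small blocks would guarantee.** With blocks of at most 8, the difference within a stratum never exceeds 4. Four symptomatic people would move the mean by 4/85 × (2 to 5) = 0.09 to 0.24 Ct.

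**The case against.** The strongest reply is that little is at risk. Allocation is random and balanced in expectation at every point, and exactly 85:85 if all 170 places are used. The imbalances above are ordinary chance variation, which the confidence interval already covers. The three tests in section 4.1.3 compare samples from one person in one session, so symptoms, variant and date are shared and largely cancel. GSS versus USS could also be made on each person's difference from the professional's OP+N sample, with much the same protection. All of this stands, and it is why the point is minor.

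A large block also makes the next allocation hard to guess. That matters at a single site where the same staff see every participant, and section 4.1.1 gives allocation concealment as its purpose. This stands as a reason against small fixed blocks. It is weaker against undisclosed blocks of varying size, and the envelopes would stay.

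An early stop may be unlikely. With about 100 visitors a day (section 3.2), 170 participants would take 34 testing days at 5% uptake and 85 at 2% (both assumed). The symptom imbalance does not depend on an early stop, however.

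Two further inferences are tempting and not supported. Because section 4.1.1 covers only GSS or USS, a reader might conclude that the order of the professional's two swabs is unbalanced. Section 2.3.2 says otherwise about its origin: "The HCP will perform the NP and OP+N sampling sequentially in a previously randomized order". How that order is generated is not described, but its absence from section 4.1.1 does not show imbalance. A reader might also credit the 3% to 17% variance gain to new blocks; it belongs to the adjustment and is available with the existing list.

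**Conclusion.** The point holds as a minor matter of precision and chance imbalance, confined to GSS versus USS. The single block enforces balance only on completion and not by symptom status or calendar time. Even at completion, section 3.4 deletes the data of anyone who withdraws consent, so the analysed arms need not be 85:85.

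The documents do not support reading this as bias, as invalid randomisation, or as a threat to the paired tests. An imbalance of 10 symptomatic people would shift GSS-USS by at most about two-thirds of a standard error. That rests on an assumed symptom effect of 2 to 5 Ct, an SD of 6 and 85 per arm. How often it would happen rests on a symptomatic share that the documents do not state. The calendar-time part is not quantified, because they give no trend in Ct over the recruitment period.

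The change is worth making because it is cheap and the analysis as written does not clearly make up for the missing balance.

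**What to change.** In section 4.1.1, replace the single block by permuted blocks of undisclosed, randomly varying size (for example 4 and 8), stratified by symptom status, and keep the sealed opaque envelopes. Symptom status must then be recorded before the envelope is opened.

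In section 4.1.4, prespecify GSS versus USS as a linear model on Ct, or on each participant's difference from the professional's OP+N sample, with symptom status as a covariate, in place of logistic regression. Add symptom status to Shell Table 1.

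The cost is a new list, two envelope sets instead of one, and slight predictability at block ends. The sample size stays at 85 per group. If the sponsor prefers to keep the block of 170, the linear model should still be adopted, with calendar time added as a covariate; it delivers the precision gain without any change to the list.

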#### 4.1.2 Sample size

The SD of the mean of Ct values for RT-PCR analysis of multiple samples is not clearly defined in the literature and varies between studies.

If there is truly no difference between the standard and experimental treatment, then 85 patients per group are required to be 90% sure that the lower limit of a one-sided 97.5% confidence interval (or equivalently a 95% two-sided confidence interval) will be above the non-inferiority limit of -3.

We, therefore, estimated a standard error of six that accounts for this variance. In addition, the limit of non-inferiority was set at three according to clinical significance.

Results will be stratified by symptom status, age, and sex.

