Studies comparing self-sampling were published, but none compared autonomous self-testing with guidance by healthcare specialists to sampling by healthcare professionals in a randomized controlled trial. Non-inferiority of oral + nasal vs. nasopharyngeal sampling has been proven. However, the question of whether telemedically supervised testing with SARS-CoV-2 Rapid Antigen Tests is non-inferior to the same tests being carried out by trained personnel in test centers is still open for debate.

With this study, we aim to compare and evaluate the reliability and sampling quality of self-performed rapid tests for professional use compared to professional sampling by healthcare personnel. This will be done by comparing cycle threshold (Ct) values of both housekeeping genes and SARS-CoV-2.

A solution that builds on the capacity of existing laboratories may be implemented with a high level of safety and minimizes the risk of transmission in rural areas. This fuels hope that medical personnel will be relieved of the burden of jointly managing the pandemic as a national and global challenge.

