## 2.2 Primary and secondary endpoints

The Ct-value is defined as the number of cycles required for a signal to cross the detection threshold and can be used as a surrogate for sampling quality, as it allows to quantify the amount of material that is being extracted.

Primary endpoints:

- Concordance of positive/negative samples in antigen tests with GSS, USS, and HCP-based samples.

Secondary endpoints:

- Housekeeping gene Ct comparison based on sampling method between samples based on GSS, USS, or HCP
- ORF1ab/RdRp-, E-, N-, and S genes Ct value comparison based on sampling method between samples based on GSS, USS, or HCP
- Qualitative analysis of perceived sampling accuracy established with a short form
- Detected variant of concern
- Case report form (CRF) assessing basic demographics and variables of interests as indicated separately in the CRF form
- Prevalence of variants of concern
- Immunization status
- Travel destinations in the passed three months
- n of people in which a nasopharyngeal sampling is possible correctly (ratio)

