### 2.3.1 Piloting

In order to assess the sampling quality by HCP or telemedically guided self-sampling, Ct values obtained in RT-PCR analysis of a COVID-19 assay, a housekeeping gene can be used for reference.

Hence, for the first part of the study, we will recruit 10 people in which we will perform an OP+N sampling at two-time points, 15 minutes apart, and compare the Ct values of these two values to calculate the standard deviation and see if the produced  $SD \cdot 1.96 / \sqrt{\text{Sample size}}$

equals the margin of error. Our 95% confidence interval (CI) will be standard deviation (SD) $\pm$  the margin of error.

Alternatively, we will pool confirmed RT-PCRs of two/three swab samples into one and spike them with SARS-CoV-2 standard. Next, we do as many repeats of the same sample on RT-PCR comparing housekeeper and SARS-CoV-2 genes. The advantage here is that we will have controlled starting biological material and the resultant SD / 95% CI will concern only the analytical and laboratory process variability. With the first approach, we will test SD of the swab procurer too, along with the interference coming from the analytical process (lab, instruments, sample storage).

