### 4.1.3 Hypothesis

Primary outcome

*NP HCP vs OP+N HCP*

H0:  $\mu_e - \mu_s \leq -d \rightarrow \mu(\text{NP HCP ct}) - \mu(\text{OP+N HCP ct}) \leq -3$

H1:  $\mu_e - \mu_s > -d \rightarrow \mu(\text{NP HCP ct}) - \mu(\text{OP+N HCP ct}) > -3$

*OP+N HCP vs OP+N GSS*

H0:  $\mu_e - \mu_s \leq -d \rightarrow \mu(\text{OP+N HCP ct}) - \mu(\text{OP+N GSS ct}) \leq -3$

H1:  $\mu_e - \mu_s > -d \rightarrow \mu(\text{OP+N HCP ct}) - \mu(\text{OP+N GSS ct}) > -3$

*OP+N HCP vs OP+N USS*

H0:  $\mu_e - \mu_s \leq -d \rightarrow \mu(\text{OP+N HCP ct}) - \mu(\text{OP+N USS ct}) \leq -3$

H1:  $\mu_e - \mu_s > -d \rightarrow \mu(\text{OP+N HCP ct}) - \mu(\text{OP+N USS ct}) > -3$

Secondary outcome:

We will stratify the primary outcome by viral load (low, medium, high).

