### 4.1.4. Statistical test

A variant of a paired student t test or Wilcoxon test (if non-normal distribution) with exchange of null and alternative (relaxed) hypotheses will be used as a non-inferiority test to assess differences in cycle threshold (Ct, considered as a log2-transformed measure of the amount of viral RNA load) between the NP and OP/N samples (HCP and GSS). Stratification for possible confounders will be done using logistic regression.

In order to show agreement between the approaches and estimate the limits of agreement and those are not too large, different graphical methods, such as Bland Altman diagrams will be used to show agreement between the approaches.

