### 4.2. Handling of missing data

Analysis is based on intention-to-treat assumption. Collected data until drop-out will be included for further analysis.

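### The 85 per group assumes a Ct from every participant; if viral Ct is tested, the stated 90% power has no basis, and no rule covers a swab without detected virus

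*Combined protocol and SAP*

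**What the plan says.** - **Sample size (4.1.2).** With no true difference, "85 patients per group are required to be 90% sure that the lower limit of a one-sided 97.5% confidence interval" exceeds the limit of -3. The spread is given as a standard error of six. Section 4.1.1 randomises a block of 170, which is 2 x 85 with no inflation.
- **Which Ct.** The hypotheses in 4.1.3 are written for mean Ct without a gene. Section 4.1.4 describes the tested Ct as a log2 "measure of the amount of viral RNA load". Section 1 announces "comparing cycle threshold (Ct) values of both housekeeping genes and SARS-CoV-2". Section 2.2 lists "Housekeeping gene Ct comparison based on sampling method between samples based on GSS, USS, or HCP" and, separately, Ct for ORF1ab/RdRp, E, N and S. Section 2.3.1 refers to "Ct values obtained in RT-PCR analysis of a COVID-19 assay, a housekeeping gene can be used for reference".
- **Test (4.1.4).** "A variant of a paired student t test or Wilcoxon test (if non-normal distribution"), turned into a non-inferiority test.
- **Population (3.1, 3.2).** Test-station visitors are enrolled whether or not they have symptoms. Recruitment ends at the sample size or a calendar date, not at a number of positives. No positivity is assumed anywhere.
- **Missing data (4.2).** Intention to treat, and "Collected data until drop-out will be included for further analysis". A swab in which no virus is found is not mentioned.
- **Rank of the endpoint.** Section 4.1.3 places the Ct hypotheses under the primary outcome. Section 2.2 makes antigen-test concordance primary and every Ct comparison secondary.

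**The concern.** A viral Ct exists only where virus was detected. In a mixed testing population many participants may have none, and some infected participants will have it on one swab but not the other. A calculation that counts all 85 per arm as contributing a value therefore does not describe a viral-Ct test.

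Two things are at stake. The first is the power figure: for a paired viral-Ct test it depends on the fraction positive and on the within-person correlation, and the plan gives neither. The second is the direction of error. A paired t test on observed Cts can use a participant only if both swabs gave a value. If self-sampling is truly worse, most of the pairs lost are those in which only the self-swab missed the virus, which is the failure the trial is meant to detect. With neither the gene nor the handling of undetected swabs fixed, both could be settled after the data are seen.

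**Working it through.** **1. Reproduce the 85.** Inputs from 4.1.2: margin 3, true difference 0, one-sided 0.025, power 90%, and six read as the SD.

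n per group = 2 x (1.960 + 1.2816)^2 x 36 / 9 = 84.06, rounded up to 85. Two-group power with 85 per group is 90.3% (normal approximation) or 90.0% (noncentral t). Every participant is counted as giving a Ct.

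**2. Power of the planned paired test.** SD of the differences = 6 x sqrt(2(1 - rho)); power from the noncentral t with n - 1 degrees of freedom. The correlation rho and the 20% positive on both swabs are assumptions: 0.20 x 85 = 17 pairs for GSS or USS against HCP, and 0.20 x 170 = 34 pairs for NP against OP+N by HCP.

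| rho | SD of differences | Pairs for 90% | As % of 85 | As % of 170 | Power, 17 pairs | Power, 34 pairs |
|---|---|---|---|---|---|---|
| 0 | 8.49 | 87 | 102.4 | 51.2 | 28% | 52% |
| 0.5 | 6.00 | 44 | 51.8 | 25.9 | 49% | 81% |
| 0.7 | 4.65 | 28 | 32.9 | 16.5 | 71% | 95% |
| 0.8 | 3.79 | 19 | 22.4 | 11.2 | 86% | 99% |

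If all 85 pairs are evaluable, power is 89.7% at rho 0 and at least 99.5% from rho 0.5. So 85 and 90% do not belong together for the paired test, with or without negatives.

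**3. Effect of using complete pairs only.** Simulation, 40,000 replicates per setting. All settings are assumed: person-level Ct normal with mean 24, 27 or 30 and variance 36 x rho; swab error variance 36 x (1 - rho); rho 0.5 or 0.7; detection limit 35, 37 or 40; self-swab truly 3 Ct higher, so non-inferiority is false. Pairs with both Cts below the limit are kept and the mean of HCP minus self is tested against -3.

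- One-sided error, nominally 2.5%: about 2.6-7% with 17 infected and 3-11% with 34.
- Mean Ct at least 10 below the limit: about 3-4.5% and 3-6%.
- Observed deficit: 2.1 to 2.95 instead of 3.
- Worst setting (mean 30, limit 35, rho 0.5, 34 infected): on average 8.0 pairs are lost because only the self-swab missed, against 2.4 because only the HCP swab missed.
- Equal swabs, same setting: mean difference 0.0. About 23 pairs remain, and power is 75% instead of 81%.
- Same setting, deficit still 3 on average, but self-swab error variance 27 against 9 for HCP: error about 37%. If instead 25% of self-swabs fail by 12 Ct: about 49%.

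**4. Does a censored analysis help?** Bivariate normal likelihood with common SD, undetected swab right-censored at the limit, conditional on at least one detection, t reference, 4,000 replicates. In the worst setting, error with 17 / 34 infected is 1.9 / 2.7%, against 6.4 / 10.6% for complete pairs on the same data sets. Power with equal swabs is 42.5 / 75.6% against 42.8 / 75.6%. In a milder setting (mean 27, limit 37, rho 0.7), error is 2.3 / 2.6% against 3.7 / 5.3% and power 68 / 95% against 70 / 95%. These data were generated from the model being fitted. In the unequal-variance and failed-swab settings of step 3, the same likelihood has error of about 6% and 11%: no longer nominal, but far below complete pairs.

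**The case against.** **The tested Ct may be the housekeeping gene.** Section 2.2 presents Ct as a surrogate for sampling quality and 2.3.1 points to a housekeeping gene. If every adequate swab yields that Ct (an assumption), there is no shortfall. This stands, and is why the point is conditional. It is also fair that stratifying by viral load does not make the outcome viral, since section 2.1 treats viral load as something that may modify the difference. The case for viral Ct rests on the description in 4.1.4, which no other section overrides.

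**Pairing may restore the power.** It may: at correlation 0.8, 19 pairs suffice. The section 2.3.1 pilot, with repeat OP+N swabs in 10 people, could inform the SD of the differences. But the plan does not use it for this, and it says nothing about positivity.

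**The plan never says that incomplete pairs are dropped.** Correct. A reader might infer a deletion rule; there is none. Section 4.1.4 also allows a Wilcoxon test, in which an undetected swab could be ranked worst. What stands is that the rule is unspecified and that a paired t test on observed values cannot use such pairs.

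**The bias figures are all assumption.** They are, and the bias is small when Ct lies well below the limit. The unnamed Ct, the unsupported power and the absent rule do not depend on its size.

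**Conclusion.** The point holds in conditional form. The 85 is correctly calculated for two independent groups with SD 6 in which everyone gives a Ct, and it can stand for housekeeping Ct. For viral Ct the 90% is unsupported. At an assumed 20% positive on both swabs, every correlation tried leaves the GSS and USS comparisons below 90%, while NP against OP+N by HCP passes 90% at correlation 0.7 and 0.8.

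A reader might conclude that the trial is underpowered. The documents do not support that: without positivity and correlation, power is unknown rather than low. Nor can the statement be rescued by reading 85 and 90% as evaluable pairs, which step 2 shows to be wrong for the paired test.

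The bias from complete pairs runs towards non-inferiority only if self-sampling is truly worse. It is modest in most settings tried, and large if self-swabs are more variable or sometimes fail.

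Severity is should-fix. One might call it critical because 4.1.3 labels these hypotheses primary, but section 2.2 lists all Ct comparisons as secondary.

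**What to change.** **(a) Sections 4.1.2 and 4.1.3.** Name the Ct (gene) tested. State that 85 per group is the independent two-group figure and assumes a Ct from every participant; do not relabel it as evaluable pairs. If viral Ct is tested, replace the 90% with paired-test power over a stated range of positivity and SD of the differences, which the pilot's repeat swabs can inform. Give it separately for the one-arm comparisons (85) and for NP against OP+N by HCP (170).

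**(b) Sections 4.1.4 and 4.2.** For each viral-Ct comparison, pre-specify that participants with at least one of the two compared swabs detected are included, and that an undetected swab is right-censored at the assay's last cycle rather than dropped. One suitable method is a bivariate censored-normal likelihood conditional on at least one detection. Let the variances differ by sampling method, and state that error control relies on the model. Report one-sided misses per method. Keep complete pairs and worst rank as sensitivity analyses; worst rank does not estimate the mean difference to which the margin of 3 applies.

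**(c)** Keep housekeeping-gene Ct as the planned analysis in all participants.

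**Cost.** Wording and one extra analysis, with no added swabs or participants. In the settings checked in step 4 the censored analysis lost at most about 3 points of power against complete pairs. The sponsor must commit to an assumed positivity and SD of the differences, and the viral-Ct power then stated may fall below 90%.
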